### *Exclusion criteria*

- Visually impaired
- Motorically impaired
- Cognitively impaired

## Criteria and procedures for subject withdrawal or loss to follow up

*When and how to withdraw a subject from the clinical investigation or stop the use of the investigational device*

Clients participate in this study voluntarily and have the right to withdraw from the study at any time they want. If they choose to withdraw they will be asked to delete the ALICE app from their smartphone or tablet.

[figure not shown]
*Documentation of efforts to be made to trace subjects that are lost to follow up and possible reasons*  
When clients withdraw from the study, they will be asked to provide a reason as this may be of interest to the study. However, they are not obligated to provide a reason for their withdrawal.

### *Whether and how subjects are to be replaced.*

In case of withdrawal or loss to follow up, we will report this but the client will not be replaced since we have sufficient participants for the study.

## Procedures

### *Overview and estimated timing*

### *Enrolment of investigator sites*

- o 6 hearing centres and 1 university hospital (UZ Leuven) will be enrolled as an investigator site in this multicentric study. The sites will be assessed based on adequate resources, a qualified investigation team and access to an adequate number of subjects.

- For every investigator site, one local PI will be appointed. The local PI will be responsible to execute the investigation (following the study protocol) and to perform the local coordination for the study.
- In order to know if the local PI is eligible to coordinate the study, the following criteria apply
  - Experienced professionals (> 5 years of working experience) in the field of aural rehabilitation of adults with hearing impairment
  - Dutch speaking
  - Willing to become familiar with research and good clinical practice
- Once the local PI has been assigned (and approved by FAGG and EC), the protocol will be discussed and the clinical trial agreement (see Annex 8) will be signed by the local PI.
- All local PI's will have to follow an initiation training, in which following details of the study are presented and/or discussed
  - Intended use of the app
  - Content of the investigator's brochure (IB)
  - Instructions for use of the ALICE app, with aids on training with the app, including set-up and internal calibration
  - Recruitment protocol
  - Enrolment protocol with ICFs for the clients
  - Study programme with study protocol (=CIP), in which instructions are included to uniformly assess and document clinical findings (eCRF)
  - GCP (see GCP protocol)
  - Quality check of the in-house equipment that will be used
  - Coordination & assistance
  - Risk management

#### *Recruitment of clients*

- Local PIs will be responsible for the recruitment of patients. Before they start with recruiting they will be instructed with clear inclusion and exclusion criteria (see 3.5.6.2 Subjects)
- The number of clients that should be enrolled will be in the range of 20-30 for every investigator site
- The recruitment period is a fixed period over a time span of 12 weeks or when 20 to 30 clients are recruited (start of the study + 12W), after that period no clients can enter the study.

#### *Enrolment of clients*

- Clients who match the criteria, will receive a brief introduction about the study, which may or may not include the ALICE app. If they are interested to participate in the study, they will receive an information brochure about the study programme, in which a more detailed description is provided (details about the course of the study, the 2 visits (at 0 and 8 weeks), the duration of the study and their rights and responsibilities.) They will also be informed that they will be assigned randomly to one of the two groups.
- If clients agree to participate in the study they will sign an informed consent form.
- A complete list of clients who wish to participate for each investigational site is sent to the KU Leuven researchers at the end of the recruitment period.
- After being stratified by age clients will be randomly assigned to one of the two groups by a KU Leuven researcher using an automatic seed generator:
  - 1 group will receive the standard of care

- 1 group will receive the standard of care with additional support of the ALICE app

	Responsible	Accountable
Clients match the criteria	Local PI	KUL PI
Clients get a brief introduction about the app and the goals of the study; when interested they receive a detailed information brochure	Local PI	
Clients sign an Informed Consent	Local PI	KUL PI
Clients are enrolled in the study	Local PI	KUL PI
Allocation of groups and randomization	KUL PI	KUL PI

*The study program and test protocol*

- Onboarding procedure: once the clients are enrolled they will receive a standard onboarding procedure, which will be led by the local PI. Within this procedure following points/formalities will be discussed with their client:
  - The study programme/course of the study
  - Appointment schedule to perform the tests
  - Procedure to follow in case of change
  - Contact information in case of questions
  - Risk & Safety management (see safety section), with special attention to following procedures:
    - Procedure to control the loudness of the stimuli provided by the app
    - Procedure to follow to ensure safe data management (compliant with GDPR)
    - Procedure to follow in case of adverse events and/or device malfunction
    - Rights and responsibilities
- Installation of the app
  - Intended use of the app
  - Compatibility of the app with personal (streaming) devices,
  - Instruction to use the app
  - First installation and set-up of account
- Test protocol (see below and Fig. 4)

*Description of all the clinical-investigation-related procedures that subjects undergo during the clinical investigation including any deviation from normal clinical practice*

Below, the timeline of the test protocol is presented: After allocation to a treatment group, a client will be assessed with speech in noise and questionnaires (Figure 4), followed by 8 weeks use of the ALICE app. The same outcome measures will be assessed at the final appointment to evaluate the benefit of the intervention.

[figure not shown]

Figure 4. Timeline of the test protocol.

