### 3.5.6.2. Research ARM 1 (approved by EC on 25/08/2022 – ref. CIV-22-06-039801)

**Description of the design type of clinical investigation to be performed (e.g. comparative double-blind, parallel design, with or without a comparator group) with rationale for the choice**

The study design is a randomized controlled clinical trial (RCT) which is the golden standard for ascertaining the efficacy and safety of a new treatment or intervention. The goal of the current RCT is to demonstrate the superiority of the ALICE app, as a new intervention over the existing standard of care.

In this RCT two groups will be compared:

- (1) A group that receives the standard of care, which is defined as followed:
  - a. Persons with a moderate to profound HI who are provided with a hearing aid
  - b. Persons with a profound to severe HI who are provided with a cochlear implant and concomitant rehabilitation. Most persons with a cochlear implant receive intensive rehabilitation during the first 6 months after their implantation. Afterwards, they mainly return for mapping of the device but not for listening training therapy.
- (2) A group that receives the standard of care, supplemented with the ALICE app, to be used as a home-based monitoring, training and counselling tool.

Description of the measures to be taken to minimize or avoid bias, including randomization, concealment of allocation, blinding/masking, assessment of blinding plan and management of potential confounding factors

For each investigator site clients will be recruited by the local principal investigator (PI) of the study (HCPs working in the hearing centre or university hospital). Once the HCP has recruited the required number of clients, they will send the list of clients to the KU Leuven researcher who will divide the clients randomly across the two groups (standard of care/additional use of ALICE). Randomisations of these two groups will be stratified according to age and will be done automatically with an automatic seed generator.

We foresee a few possible confounding factors:

- Medical confounding factors
  - o Type and degree of HI
  - o Comorbidities such as high blood pressure, diabetes, stroke, visual acuity, cognitive abilities
- Methodological confounding factors

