#### *Enrolment of clients*

- Clients who match the criteria, will receive a brief introduction about the study, which may or may not include the ALICE app. If they are interested to participate in the study, they will receive an information brochure about the study program, in which a more detailed description is provided (details about the course of the study, the 2 visits at 0 and 8 weeks, the duration of the study and their rights and responsibilities). They will also be informed that they will be assigned randomly to one of the three groups.
- If clients agree to participate in the study they will sign an informed consent form.
- A complete list of clients who wish to participate for each investigational site is sent to the KU Leuven researchers at the end of the recruitment period.
- After being stratified by age, clients will be randomly assigned to one of the two groups by a KU Leuven researcher using an automatic seed generator:
  - 1 group will receive the standard of care
  - 1 group will receive the standard of care with additional support of the ALICE app (French version)

	Responsible	Accountable
Clients match the criteria	Local PI	KUL PI
Clients get a brief introduction about the app and the goals of the study; when interested they receive a detailed information brochure	Local PI	
Clients sign an Informed Consent Form	Local PI	KUL PI
Clients are enrolled in the study	Local PI	KUL PI
Allocation of groups and randomization	KUL PI	KUL PI

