### 3.5.7. Statistical design and analysis

#### 3.5.7.1. Sample size

HCPs from the hearing centres participating in the first, second and third arm of the study will include a total of 390 hearing aid users (150 in the first arm, 120 in the second arm and 120 in the third arm). HCPs from UZ Leuven will include 30 CI users for the first arm only. Clients will be equally divided among participating investigation sites. After being stratified by age, they will be randomly assigned to two groups of approximately 195 hearing aid users (75 in the first arm, 60 in the second arm and 60 in the third arm), and two groups of 15 CI users (first arm only). One group will receive the standard of care, the other group will receive the standard of care supplemented with the ALICE app (The Dutch version in both the first and second arm the French version in the third arm).

Scientific literature was consulted to estimate the group size needed for our RCT and a power analysis was conducted to confirm the effect size for this sample.

Power analysis conducted with the G\*Power software (Erdfelder et al., 2009) indicated that a total sample of at least 76 persons is needed to detect differences in speech understanding in noise outcomes between the two treatment groups with a low to medium effect size ( $d = 0.25$ ) to have statistical power of 95% using a repeated measures ANOVA ( $\alpha = 0.05$ ). We will be able to recruit more clients via the hearing centers (between 15 and 30 persons per hearing center). We estimate that, for all three arms of the study, 390 persons with a HA will take part in the trial and, for the first arm of the study only, about 30 persons with a CI. This larger number accounts for clients being lost to follow-up during the study.

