#### 3.5.7.2. Statistical analysis

Statistical analyses will be performed using either the R programming language and statistical environment (R Core Team, 2017) or IBM SPSS 27. Potential missing data will be replaced using multiple imputation (in SPSS).

Data for hearing aid users and cochlear implant users will be analysed separately. Potential relations between outcomes will be determined in a within-subject design, i.e., baseline session outcomes will be compared to the final session outcomes, with a repeated measures ANOVA ( $\alpha = 0.05$ ). We will correct for multiple comparisons using Dunn post-hoc tests with Holm correction (Dunn, 1961).

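### Randomisation is stratified by age, and in Arms 1 and 3 works from per-site lists, but the planned repeated measures ANOVA includes neither age nor site, so it does not reflect the randomisation and may lose some precision

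*Combined protocol and SAP*

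**What the plan says.** - **Stratification.** For Arm 1, section 3.5.6.2 says: "Randomisations of these two groups will be stratified according to age", and under Enrolment of clients: "After being stratified by age clients will be randomly assigned to one of the two groups". Sections 3.5.6.3 (Arm 2), 3.5.6.4 (Arm 3) and 3.5.7.1 also name age and no other factor. The text gives no age cut-points and no blocking method.
- **Lists.** In Arms 1 and 3, Enrolment of clients says: "A complete list of clients who wish to participate for each investigational site is sent to the KU Leuven researchers". This happens at the end of recruitment, and a KU Leuven researcher then randomises. Arm 2 has a rolling start and no such lists.
- **Sites.** Clients are to be spread equally over sites. That gives about 150/6 = 25 hearing aid users per centre in Arm 1, 120/6 = 20 in Arm 2 and 120/8 = 15 in Arm 3. The 30 cochlear implant users in Arm 1 all come from one hospital.
- **Analysis.** Section 3.5.7.2 says "baseline session outcomes will be compared to the final session outcomes, with a repeated measures ANOVA", with hearing aid and cochlear implant users analysed separately. It names no age term, site term or other covariate.

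**The concern.** An analysis should carry the factors used to constrain the randomisation. Stratifying balances the groups on age and so removes age from the true sampling variation of the treatment contrast. A model without age still counts that variation as error, so the test is conservative and the confidence intervals are wider than they need be.

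Site has a similar claim. The local investigator runs the test protocol, testing uses the site's own audiometer, and the local team delivers the standard of care that serves as comparator. If improvement over the study period differs between centres, a site term removes that variation.

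At stake are precision and a correctly sized test. The validity of the comparison is not threatened.

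**Working it through.** **1. The plan's own figure.** Section 3.5.7.1 "indicated that a total sample of at least 76 persons is needed" "to have statistical power of 95% using a repeated measures ANOVA", with effect size 0.25 and alpha 0.05. For the group-by-time test with k groups, m sessions and correlation ρ between sessions:

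λ = f²·N·m/(1−ρ), df1 = (k−1)(m−1), df2 = (N−k)(m−1).

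- k = 4, m = 2, ρ = 0.5, f = 0.25, N = 76: λ = 0.0625·76·2/0.5 = 19, df 3 and 72, power 0.959. N = 72 gives 0.948.
- k = 2, m = 2, ρ = 0.3, N = 76: λ = 0.0625·76·2/0.7 = 13.57, power 0.953.
- k = 2, m = 2, ρ = 0.5: N = 54 is enough.

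So 76 is reproduced if 0.25 is Cohen's f, under settings that the plan does not state. With 120 or more clients, either setting that gives 76 yields power of about 0.996 or higher, without adjustment. The plan labels 0.25 as d. Read that way (f = 0.125, k = 2, ρ = 0.5), the same test needs 210.

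**2. Which variance counts.** With two sessions, the group-by-time F test equals the squared t test on change (final minus baseline). Stable differences between ages or centres cancel. Only their effect on change matters, so a main effect of age or site without its time interaction would not alter this contrast.

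**3. Precision.** Let R² be the share of the variance of change explained by age and site. The documents do not give it, so I assume 5, 10 and 20%. With groups balanced within strata and sites, the standard error is multiplied by √(1−R²). If such balanced factors are left out, the true two-sided error is 2{1 − Φ(1.96/√(1−R²))}. The power column takes 150 hearing aid users and an assumed difference of 0.5 SD of change; unadjusted power is 0.865.

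| R² | √(1−R²) | SE reduction | 1.96/√(1−R²) | True error if omitted | Power, adjusted |
|---|---|---|---|---|---|
| 5% | 0.975 | 2.5% | 2.011 | 0.044 | 0.881 |
| 10% | 0.949 | 5.1% | 2.066 | 0.039 | 0.898 |
| 20% | 0.894 | 10.6% | 2.191 | 0.028 | 0.928 |

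**4. Balance within centres if lists are pooled.** Fix the totals at 1:1 in each arm, assume equal site sizes and ignore the age strata. The number allocated to ALICE in one centre is then hypergeometric.

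| Arm | Centres × clients | Split or worse | One given centre | At least one centre |
|---|---|---|---|---|
| 1 | 6 × 25 | 17:8 | 0.078 | 0.36 |
| 2 | 6 × 20 | 14:6 | 0.085 | 0.39 |
| 3 | 8 × 15 | 10:5 | 0.27 | 0.90 |

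If each list is randomised 1:1 on its own, this imbalance largely disappears.

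**5. What pooling does to the gain.** With site in the model, such imbalance costs on average 3.4, 4.2 and 5.9% of the information in Arms 1, 2 and 3. In Arm 3 the standard error is then multiplied by √((1−R²)/0.941), which is 1.005, 0.978 and 0.922 for R² of 5, 10 and 20%. The gain shrinks to about −0.5, 2.2 and 7.8%. Allocation within site is what secures the figures in step 3.

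**The case against.** A reader might infer that the groups will be unbalanced within centres. The documents do not show this. In the bias sections of Arms 1 and 3, recruitment, sending of the list and random division are all described site by site, and nothing says that lists are pooled. Randomising list by list is a natural reading. Under it, imbalance is no longer the issue, but site becomes an unlisted stratum that is missing from the model, so the analysis half of the point gains weight.

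A reader might also infer that audiologist or equipment effects would be confounded with the app effect. Chance imbalance under randomisation is not systematic bias. The protocol also asks for calibrated audiometers, a quality check of in-house equipment and instruction in uniform assessment. That should limit differences between centres, though it cannot rule out differences in change.

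Three further limits stand:

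- R² is assumed. Because stable differences cancel, it is probably nearer the lower end, and a share taken from the variance of the outcome itself would overstate the gain.
- On the plan's effect size read as Cohen's f, power is already close to 1, so the conclusion is unlikely to turn on this.
- Site is irrelevant for the cochlear implant users, and the argument from complete lists does not reach Arm 2.

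Arm 3's recruitment range of 15 to 20 per site might suggest a calculation with 20 clients at all eight sites. That makes 160, above the planned 120, so 15 is the consistent figure.

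**Conclusion.** The point holds as a mismatch between randomisation and analysis. Age is the declared stratum in every arm and is absent from the model; site structures the lists in Arms 1 and 3 and is absent too. The consequence is small: a standard error about 2.5 to 11% larger than necessary and a 5% test running at about 4.4 to 2.8%, if age and site explain 5 to 20% of the variance in change and are balanced between groups. With pooled lists, the precision gain from adding site is smaller, and in Arm 3 it is about nil at 5%.

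Within-centre imbalance is a possibility that the text leaves open. If lists are pooled, a 2:1 or worse split in at least one Arm 3 centre has a probability of about 90%, and a 14:6 or worse split in at least one Arm 2 centre about 39%. Neither implies bias. This is a worthwhile refinement and not a threat to the trial's conclusions.

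**What to change.** - **Section 3.5.7.2.** Write out the group-by-time contrast, which that section does not name. For hearing aid users in each arm, include age stratum and site, each with its interaction with time, or equivalently as covariates in a model for change. For the cochlear implant users include the age stratum only.
- **Section 3.5.6.4 (Arm 3).** Have the KU Leuven researcher randomise each site's complete list 1:1 within age stratum.
- **Sections 3.5.6.2 to 3.5.6.4.** State whether lists are or were randomised separately or pooled, and give the age cut-points and the method of balancing.

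For Arm 2 I suggest the model terms only. Clients enter one by one there and sites know the allocations, so small blocks within site would make the next assignment easier to guess.

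The cost is small. Site takes 7 degrees of freedom in Arm 3 and 5 among hearing aid users in each of Arms 1 and 2, plus one fewer than the number of age strata. Some site-by-age strata will be small with 15 clients per centre, but with complete lists an odd-sized stratum is out of balance by only one client. Age and site are already known for every client, and the model terms can be fixed before analysis even where allocation is complete.

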  - o For sentence understanding in noise, procedural effects are believed to be minimal. The LIST sentence materials will be offered twice, at first and final appointment. Lists of sentences are counterbalanced and never presented twice.
  - o Potential procedural effects for the questionnaires may occur and will be controlled for by administering the questionnaires twice prior to the participants starting the training and at the end of the 8 week training period.
- Other confounding factors such as lifestyle factors

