The **SSQ12** is a short version of the validated Speech, Spatial and Qualities of Hearing Scale. This short form was developed for use in clinical research and rehabilitation settings. (Noble et al., 2013). Participants score each questions on a ruler (visual analogue scale) from 0 to 10. Questions were translated to Dutch.

The **IOI-HA** (International Outcome Inventory for Hearing Aids) evaluates the daily use of the hearing aid, as well as the perceived benefit and satisfaction with the hearing aids or cochlear implants. The IOI-HA consists of 7 questions and has been validated in Dutch (Kramer et al., 2002).

**Equipment to be used for assessing the clinical investigation variables and arrangements for monitoring maintenance and calibration**

*Equipment used/needed to perform test protocol*

- Speech in noise testing: part of the standard of care
  - o Audiometer (calibrated): available at the investigational sites
- Questionnaires: online/tablet
  - o Clients will be able to fill out the questionnaires on a tablet (provided by the KU Leuven researchers to the investigational sites) or on their own computer through a website.
- The app will be used on the clients' personal smart device (device compatibility will be described in IB)
- Feedback: documented in word files

**Clinical investigation sites: number, location and if appropriate differences in clinical investigation site characteristics**

A list of participating clinical investigation sites and their locations will be provided at a later stage.

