## Monitoring plan

*General outline of the monitoring plan to be followed, including access to source data and the extent of source data verification planned*

In accordance with ICH-GCP E6(R2) the Sponsor is responsible for monitoring the Trial to ensure compliance with GCP and current legislation, and to verify, among other requirements, that proper written informed consent has been obtained and documented, that the Trial procedures have been followed as shown in the approved protocol, and that relevant Trial data have been collected and reported in a manner that assures data integrity. To this end Source Data will be compared with the data recorded in the (e)CRF. A risk-based approach will be applied to determine the extent of monitoring activities and monitoring of the Trial will be performed by qualified individuals (independent from the site Trial staff), as applicable.

- **Coordination & monitoring plan**

- o Project management and on-site monitoring visits

The Coordinating Investigator ([name], KUL) will supervise: the recruitment and the enrolment of the study participants (including the verification of the ICF procedure), the implementation of the study protocol at the investigational sites, the quality of the data collection, the achievement of the study goals, and the use of the ALICE app according to the CIP.

The test protocol will be performed by the local PI. The local PI can rely on support and assistance of the Coordinating Investigator at any given time. The Research Manager will schedule regular monitoring visits with the local PI. All monitoring activities will be documented in a written report according to ISO14155.

- o Project support

When clients need additional support their first contact point will be their local PI. When the support needed is related to their hearing or hearing aids, the local PI will help them out through their standard of practice (standard care path).

When the support needed is related to the use of the app, the local PI will contact the Coordinating Investigator. The Coordinating Investigator will provide the local PI with additional support, if needed technical support will be provided by our in-house developers.

- o Safety evaluation & reporting

- Adverse events, device deficiencies, and withdrawals will be reported and documented (see section 'Subjects' + withdrawal procedure section 3.5.6.2).
- Data collection

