    - Procedure to follow in case of adverse events and/or device malfunction
  - Rights and responsibilities
- Installation of the app
  - Intended use of the app
  - Compatibility of the app with personal (streaming) devices,
  - Instruction to use the app
  - First installation and set-up of account
- Test protocol (see below and Fig. 4)

*Description of all the clinical-investigation-related procedures that subjects undergo during the clinical investigation including any deviation from normal clinical practice*

Below, the timeline of the test protocol is presented after allocation to a treatment group a client will be assessed with speech in noise and questionnaires (Figure 5). Followed by 4 to 6 weeks use of the ALICE app. The same outcome measures will be assessed at the end of the hearing aid trial period to evaluate the benefit of the intervention.

[figure not shown]

Figure 5. Timeline of the test protocol of the second research arm

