#### *The study program and test protocol*

- Onboarding procedure: once the clients are enrolled they will receive a standard onboarding procedure, which will be led by the local PI. Within this procedure following points/formalities will be discussed with their client:
  - The study program/course of the study
  - Appointment schedule to perform the tests
  - Procedure to follow in case of change
  - Contact information in case of questions
  - Risk & Safety management (see safety section), with special attention to following procedures:
    - Procedure to control the loudness of the stimuli provided by the app
    - Procedure to follow to ensure safe data management (compliant with GDPR)
    - Procedure to follow in case of adverse events and/or device malfunction
  - Rights and responsibilities
- Installation of the app
  - Intended use of the app
  - Compatibility of the app with personal (streaming) devices,
  - Instructions to use the app

- First installation and set-up of account
- Test protocol (see below and Fig. 6)

*Description of all the clinical-investigation-related procedures that subjects undergo during the clinical investigation including any deviation from normal clinical practice*

Below (Figure 6), the timeline of the test protocol is presented: After allocation to a treatment group a client will be assessed with a speech in noise test and questionnaires, followed by 8 weeks use of the ALICE app. The same outcome measures will be assessed at the final appointment to evaluate the benefit of the intervention.

*Figure 6. Timeline of the test protocol.*

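### In all three arms baseline is taken after allocation, with no masking described and no rule keeping the client or the local PI from knowing the group at that point

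*Combined protocol and SAP*

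**What the plan says.** The study-procedure text gives one sequence in every arm.

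- Arm 1 (3.5.6.2): "After allocation to a treatment group, a client will be assessed with speech in noise and questionnaires", followed by 8 weeks of app use.
- Arm 2 (3.5.6.3): "after allocation to a treatment group a client will be assessed with speech in noise and questionnaires", followed by 4 to 6 weeks of app use.
- Arm 3 (3.5.6.4): "After allocation to a treatment group a client will be assessed with a speech in noise test and questionnaires", followed by 8 weeks of app use.

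In each arm the same measures are repeated at the end. The bias section of each arm is headed "concealment of allocation, blinding/masking, assessment of blinding plan and management of potential confounding factors". The text beneath covers age-stratified randomisation and a list of confounders. It does not mention masking of client, practitioner or assessor.

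Each arm has a "standard onboarding procedure, which will be led by the local PI", in which app installation is listed before the test protocol. Each monitoring plan adds: "The test protocol will be performed by the local PI".

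To control procedural effects, the bias sections also plan "administering the questionnaires twice prior to the participants starting the training" and again at the end of training. Section 3.5.7.2 compares baseline with final-session outcomes by repeated measures ANOVA.

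**The concern.** Randomisation makes the groups comparable up to the moment of assignment. It cannot balance an influence that starts afterwards. A client who has just learned that they will, or will not, receive the app may rate their difficulties differently, and a practitioner who knows the group may present the tests differently. Either would create a baseline difference between groups that cannot be told apart from chance imbalance, and baseline is half of the planned comparison.

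Exposure differs by outcome. The questionnaires are the most exposed: "Clients will be able to fill out the questionnaires on a tablet", or on their own computer. That applies to SSQ12 and CAS in all arms and to EAS in Arms 1 and 3. The speech test uses a calibrated audiometer, with counterbalanced lists in Arm 1, and is less exposed. COSI is completed jointly by audiologist and client and rates progress after fitting. The Arm 2 counts of contact time, tests, fittings and appointments accrue during the trial period and have no baseline to shift.

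**Working it through.** The plan gives no figure on this point, so the main check is a reading of the text.

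| Question | Arm 1 (3.5.6.2) | Arm 2 (3.5.6.3) | Arm 3 (3.5.6.4) |
|---|---|---|---|
| Baseline relative to allocation | after | after | after |
| When allocation is made | after the site's list is sent at the end of recruitment | rolling start | after the site's list is sent at the end of recruitment |
| Masking described | none | none | none |
| Who leads onboarding and performs tests | local PI | local PI | local PI |
| When client or local PI learns the group | not stated | not stated | not stated |
| Visits announced to clients | 2 | 3 | 2 |

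**Does the repeated questionnaire settle it?** The phrase can mean two administrations before training, or one before and one at the end. Arm 2's three visits are compatible with two earlier sessions. In Arms 1 and 3 the two visits at 0 and 8 weeks fit less easily, although a client could complete one questionnaire at home. On either reading the timing is tied to the start of training, not to allocation, and the speech test is not covered. In Arm 1 the LIST is given at the first appointment, which is not said to precede allocation.

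**Can the effect be sized?** Only under assumptions that are not in the documents. Suppose knowledge of the group shifts baseline by b standard deviations between groups and a fraction p of that shift recurs at the final session. Assume 1:1 allocation, equal SDs, no true effect, full follow-up, and a group-by-time test equivalent to a change-score test. With baseline-final correlation r:

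- Net bias now, in size: b(1 − p).
- Net bias if baseline is taken before disclosure: pb, because the final session stays unmasked.
- The variance of the group difference in change is 8(1 − r)/N, so the noncentrality is λ = (net bias)² × N / [8(1 − r)], referred to F(1, N − 2).

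With b = 0.2, N = 120 and r = 0.5, λ = (net bias)² × 120/4 = 30 × (net bias)². The chance of a false-positive result at a nominal 5% is:

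| p | Net bias now | λ now | Rate now | Net bias after | λ after | Rate after |
|---|---|---|---|---|---|---|
| 0 | 0.20 | 1.2 | 19% | 0 | 0 | 5% |
| 0.5 | 0.10 | 0.3 | 8% | 0.10 | 0.3 | 8% |
| 0.75 | 0.05 | 0.075 | 6% | 0.15 | 0.675 | 13% |
| 1 | 0 | 0 | 5% | 0.20 | 1.2 | 19% |

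Under this model, reordering lowers the error when p < 0.5, is neutral at 0.5 and raises it above that. If the shift changes sign between sessions (p < 0), reordering helps more: at p = −0.5 the net bias goes from 0.30 (37%) to 0.10 (8%).

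The current rate also depends on the other inputs. At p = 0 and b = 0.2 it runs from 15% (r = 0.3) to 29% (r = 0.7) with N = 120. With r = 0.5 it runs from 8% for the 30 CI users to 50% if all 390 hearing aid users are pooled. Section 3.5.7.2 separates hearing aid from CI users but does not say whether the arms are analysed separately.

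**The case against.** **Allocation is not disclosure.** KU Leuven could randomise and withhold the result until baseline is done. Figures 4 to 6 and the timing overviews could not be read in the copy examined, and they are where visit order and disclosure would appear. This stands. A reader might infer that client and local PI do know the group at baseline; the documents do not say so. They show only that no rule prevents it. If the figures give another order, the prose still needs correcting.

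**Central randomisation protects the trial.** In Arms 1 and 3 it helps conceal assignments before they are made. It does not keep the group unknown at an assessment placed afterwards. Pseudonymised data for the researchers (3.5.8.3) is not masking to group.

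**The main outcome is the speech test.** Section 3.5.3.2 says so and the power analysis rests on it, so the most exposed measures are not the ones that size the trial. This limits the weight of the point. It does not remove it, because 3.5.5.1 words the primary hypothesis as what clients themselves indicate about daily listening.

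**The reordering shows no guaranteed gain.** This stands too. A reader might infer that a 19% error rate would return to 5%; the table above shows that this needs the shift to be absent at the final session, which nothing in the documents supports.

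**Who randomises in Arm 2.** The enrolment table and the prose of 3.5.6.3 disagree. That is a separate defect and adds no weight here.

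**Conclusion.** The point holds as a weakness in sequence and disclosure. All three arms put the baseline speech test and questionnaires after allocation, describe no masking, and leave unstated when the group becomes known to the client and to the local PI who tests them. The self-rated scores are the ones at risk.

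Size and direction cannot be derived from the documents. The bias could favour ALICE or hide a benefit, and a shift of equal size at both sessions would cancel. The case for change therefore rests on principle, not on a calculated gain: a baseline completed before disclosure cannot be affected by knowledge of the group, so any remaining difference there is chance, and bias from that knowledge is confined to the final assessment. This is a worthwhile, inexpensive improvement, held with medium confidence because knowledge at baseline is inferred and the figures remain to be checked.

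**What to change.** For clients not yet assessed, complete the baseline speech test and questionnaires before the group is disclosed to the client or the local PI, then disclose it and install the app at the same visit. KU Leuven randomises as planned and releases each result once the site confirms that baseline is complete. Release should not wait for eCRF entry, since 3.5.8.1 places transcription after the visit.

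In each arm, state when the client and the local PI learn the group and whether either early questionnaire administration precedes allocation. Check the text against Figures 4 to 6. Report baselines already taken after disclosure as such.

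Cost: one change of order in each arm's text and a per-client release during the first visit. KU Leuven must be reachable, or a pre-loaded release used, while the client is on site, because the supervised app session before home use (3.5.14.1) follows disclosure. The ceiling is 150 + 30 + 120 + 120 = 420 releases. Arm 1 was approved in August 2022 with a 12-week recruitment window and Arm 3 is marked as new, so the change probably reaches mainly Arm 3 and any remaining Arm 2 clients, at most 120 + 120 = 240. Baselines already collected cannot be repaired, and bias at the unmasked final assessment is not removed.
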